9.1.2 Definition of Cumulative ADAb Status

The ADAb status (positive, negative or missing) will be considered in a cumulative manner at each time point.

A study participant will be counted positive from the first visit at which the study participant achieved a positive ADAb sample result to the end of the treatment period, regardless of any missing/inconclusive or negative ADAb sample result.

If a study participant has only negative ADAb samples or only one missing/inconclusive sample with all negative ADAb samples up to that timepoint, the study participant will be classified as negative. An exception remains for the Baseline Visit where only one sample could be available. If the sample is missing/inconclusive, then the sample will be classified as being negative for the cumulative ADAb status.

Otherwise, the study participant will be classified in the missing ADAb category.

9.1.3 PK Sample Inclusion and Exclusion Rules

PK samples collected at all visits except the SFU visit and meeting the following requirements will be included in summaries and corresponding figures. Samples not meeting the following requirements will be excluded from summaries and figures, and only listed:

- For PK samples associated with Week 2: include samples collected ≥ 1 week and ≤ 3 weeks after the first BKZ dose and before the subsequent BKZ dose.
- For PK samples associated with Week 52 or the ET visit: include samples collected >14 days and <42 days after the last/previous dose received.
- For all other visits: include samples collected >14 days after the preceding dose, <42 days after the preceding dose, and no later than 1 hour after the current visit dose including unscheduled assessments as described in Section 3.1.

For the SFU visit, all concentrations obtained at the SFU visit will be included in the summary tables but will not be included in the figures.

When multiple samples meeting the criteria above are associated with the same visit (either because multiple samples were collected or due to remapping or unscheduled visits), only results from one valid sample will be included in summaries and figures using the following rules. All others will be excluded and only listed:

- For PK samples with different dates, the sample that is closest to the target visit date will be included. For samples with different dates that are the same distance to the target visit date, the sample collected prior to IMP dosing will be included.
- For PK samples with the same date, the first sample as provided in the raw data will be included.

In addition, a PK sample could be excluded in the following situations:

- Sample collected after the study participants received more than one dose of BKZ at a single visit, or multiple doses separated by a few days,
- Sample collected after the study participants received less than a complete dose at a single visit,

In each of these 2 possible scenarios, the study participants will be flagged with an appropriate protocol deviation, and the sample to be excluded will be identified based on the review of the description of the deviation.

All excluded samples will be assigned one or more reasons for exclusion:

- Sample collected out of window relative to current dose
 - For PK samples associated with Week 2: includes samples collected <1 week or >3 weeks after the first BKZ dose.
 - For PK samples associated with visits other than week 2, 52, ET, or SFU: includes samples >1 hour after the current visit dose.
- Sample collected out of window relative to previous dose
 - For PK samples associated with all visits except the Week 2 or SFU visit: includes samples collected <14 days or >42 days after the previous dose received.
- More than one sample obtained at the same visit
 - Includes all samples excluded due to multiple valid samples associated with a visit.

- Sample collected after the study participant received more than 160 mg of study drug in previous 4 week period
- Sample collected after the study participant received less than 160mg of study drug at previous visit

9.1.4 Summary of Analyses

PK variables will be summarized by treatment group (BKZ 160 mg Q4W and Placebo / BKZ 160 mg Q4W).

Bimekizumab plasma concentrations will be summarized for the above treatment groups, at each scheduled visit at which samples were taken, using the PK-PPS analysis set and based on observed values. No imputation will be used for missing samples. However, if plasma concentration measurements are below the level of quantification (BLQ), then for calculation of the derived statistics, the result will be set to $\frac{1}{2}$ of the lower level of quantification (LLOQ) (ie, $1/2*0.250 = 0.125$ ug/mL). Descriptive statistics including number of values, geometric mean, geometric mean 95% CI, geometric coefficient of variation, mean, standard deviation, median, minimum, and maximum if applicable will be calculated if at least 2/3 of the values of interest are above the LLOQ and $n \geq 3$. Otherwise, only number of values, median, minimum, and maximum will be presented.

In addition, the geometric mean of bimekizumab plasma concentration (with the 95% CI) will be plotted versus time on linear and semi-logarithmic scales. These figures will be generated overall for each treatment group.

The table summary and figures will be repeated by cumulative anti-bimekizumab antibody status as defined in Section 9.1.2, for the overall population. The figures will be produced separately for each treatment group.

All plasma concentration data will be reported in ug/mL in the tables, figures and listings.

Bimekizumab plasma concentrations will be listed for the SS. All concentrations will be listed as received prior to substitution of any BLQ values. The listing will include flags for concentrations that were excluded from the summary statistics and include the reason for exclusion as defined in Section 9.1.3.

If more than 10% of the PK concentration results have been excluded from the table summaries, the PK excluded results will be listed in a separate listing.

9.2 Immunology (Immunogenicity)

9.2.1 Anti-bimekizumab antibody

ADAb samples are analyzed when participants are on bimekizumab treatment. ADA will be assessed using a three-tiered assay approach: screening assay, confirmatory assay and titration assay. Samples confirmed as positive within the confirmatory assay will be further evaluated for the presence of neutralizing anti-bimekizumab antibodies (NAb) specific to IL-17AA, IL-17FF or both (described in the next section).

Screening, confirmatory and titer cut points of the respective assays will be determined by the bioanalytical laboratory.

9.2.1.1 Definition of ADAb Sample Status (Positive, Negative, Missing)

This will be as defined in Section 9.1.1 above.

9.2.1.2 Definition of Overall ADAb Status (Positive, Negative, Missing)

A participant's Overall ADAb Status will be derived for the following periods:

- Overall ADAb Status in the Treatment Period: Including any visit during the treatment period (as defined in Section 3.2.2). Thus, this summary will exclude data obtained at the SFU visit and will include data obtained at Baseline. This summary will display the overall ADAb status up to Weeks 16, 24 and 52 by treatment group (BKZ 160 mg Q4W, Placebo / BKZ 160 mg Q4W).
- Overall ADAb Status including SFU: Including any visit during the study. Thus, this summary will include data obtained at both the SFU visit and at Baseline.

Study participants who rolled over to the OLE study will not have a SFU visit per study protocol. For these study participants, the 'overall ADAb status including SFU' will then be considered as being identical to the 'overall ADAb status up to Week 52'.

For each time period, the participant will be classified as:

- Positive if the study participant has at least one positive sample up to the time point of interest (regardless of having missing/inconclusive data).
- Negative if the study participant has all the samples negative or only one missing/inconclusive sample with negative ADAb samples up to the timepoint of interest.
- Missing if the study participant has missed more than one ADAb result (or have more than one inconclusive sample) and all other available ADAb samples are negative up to the time point of interest.

9.2.1.3 Definition of ADAb Categories

In addition, the anti-BKZ antibody status will be further classified as outlined below:

- **Pre ADAb negative – treatment emergent ADAb negative (Category 1):** Includes study participants who are negative at Baseline and antibody negative at all sampling points (including SFU), one post-Baseline missing/inconclusive sample is allowed for study participants with pre-ADAb negative sample. This group also includes study participants who have a missing/inconclusive pre-treatment sample (eg, either missing/inconclusive or insufficient volume) at Baseline with all post-Baseline samples as ADAb negative.
- **Pre ADAb negative – treatment emergent ADAb positive (Category 2):** Includes study participants who are ADAb negative at Baseline and ADAb positive at any sampling point post treatment (including SFU). This group also includes study participants who have a missing pre-treatment sample (either missing or insufficient volume) at Baseline with one or more ADAb positive post-treatment samples.
- **Pre ADAb positive – treatment emergent reduced ADAb (Category 3):** Includes study participants who are ADAb positive at Baseline, and antibody negative at all sampling points post-treatment (including SFU).
- **Pre ADAb positive – treatment emergent unaffected ADAb positive (Category 4):** Includes study participants who are positive at Baseline and are positive at any sampling

point post-treatment (including SFU) and all post-Baseline samples have titer values < 2.07 times the Baseline titer (where 2.07 is Minimum Significant Ratio (MSR))

- **Pre ADA_b positive – treatment emergent ADA_b boosted positive (Category 5):** Includes study participants who are positive at Baseline and have at least one positive post-treatment sample (including SFU) that has titer value ≥ 2.07 times the Baseline titer (where 2.07 is Minimum Significant Ratio (MSR))

Note: For any study participant who is positive at Baseline and positive at a post-Baseline time point, but for whom titers are not available to determine treatment unaffected or treatment boosted status, the study participant will be considered as treatment boosted (ie,, Category 5), assuming no other samples are available.

- **Inconclusive (Category 6):** Includes study participants who have a positive pre-treatment sample and some post-treatment samples are missing/inconclusive, while other post-treatment samples are ADA_b negative.
- **Total treatment-emergent (Category 7 [Categories 2 and 5 combined]):** Includes study participants who are pre ADA_b negative – treatment emergent ADA_b positive (Category 2) and pre ADA_b positive – treatment boosted ADA_b positive (Category 5).
- **Total prevalence of pre-ADA_b positivity (Category 8 [Categories 3, 4, 5 and 6 combined]):** Study participants that are tested ADA_b positive at Baseline.
- **Missing (Category 9):** Includes study participants who have a negative or missing/inconclusive pre-treatment sample at Baseline and more than one post-treatment samples are missing/inconclusive, while other samples are ADA_b negative. Includes also study participants who have missing/ inconclusive pre-treatment sample at Baseline, and only one missing post-baseline sample with no ADA_b positive.

9.2.1.4 ADA_b status groups for Efficacy Endpoint Summaries

For the Efficacy Endpoint by ADA_b Summaries (described below), the following ADA_b-efficacy status groups will be defined:

- ADA_b positive - Defined as study participants having at least 2 ADA_b positive samples up to the time point of interest (i.e., excluding Baseline, excluding SFU) regardless of other ADA_b negative samples and/or missing or inconclusive samples
- ADA_b negative -Defined as study participants for whom either (1) all samples to the time point of interest are ADA_b negative and there are no missing or inconclusive samples, (2) only 1 sample is ADA_b positive and all other to the time point of interest (including Baseline) are ADA_b negative or missing/inconclusive or 3) only one sample is missing/inconclusive and the remaining ADA_b samples are negative.
- Missing - Defined as study participants who do not fulfil the criteria for one of the 2 groups listed above.

ADA_b data from Baseline up to the timepoint of interest will be used to derive the ADA_b-efficacy status groups.

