9.2.2.2 Efficacy Endpoint by ADA^b Summaries

Several figures, tables, and listings will be created:

- Figures will summarize efficacy response (ASAS40 and ASAS20 responders based on NRI) versus ADA^b titer quartiles. The x-axis will display the ADA^b titer quartiles at Week 16 (categorized as negative, Q1, Q2, Q3 and Q4) and the y-axis will display percentage of ASAS40 (or ASAS20) responders at Week 16.

The plots will therefore display the percentage of ASAS40 (or ASAS20) responders as a function of the number of study participants within each ADAb titer categories. Study participants with negative ADAb results at Week 16 will be included in the ‘negative’ category on the x-axis. This plot will include data from study participants only randomized to BKZ 160 mg Q4W.

For each efficacy endpoint (ASAS40 and ASAS20 responders), the figure will be repeated using Week 24 data and then using Week 52 data. These figures will include all study participants receiving BKZ and will be split by treatment group (BKZ 160 mg Q4W throughout, Placebo/ BKZ160 mg Q4W starting at Week 16). Thus, 2 figures per efficacy variable and time point will be presented.

- Two figures will summarize efficacy response (ASAS40 responders based on NRI) over time for each treatment group (Placebo/BKZ 160 mg QW4 (starting at Week 16) and BKZ throughout) by the ADAb-efficacy status groups defined above in Section 9.2.1.4 (3 lines per plot).

If $\geq 95\%$ of study participants are included in the non-missing groups, the missing group will not be displayed on the figure.

The first two figures will present data up to Week 24. Two similar figures will present data up to Week 52. These four figures will then be repeated for the ASAS20 endpoint. For each figure, the ADAb-efficacy status groups will be calculated based on data up to the timepoint of interest.

An additional figure for BKZ 160 mg Q4W group only will be generated for ASAS40 and ASAS20 with data up to Week 16.

The percent of study participants in each of the ADAb-efficacy status groups considered for efficacy sub-group analyses will be summarized.

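### The antibody-status groups used for the efficacy summaries treat missing samples and Baseline inconsistently, so some participants get the wrong label

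*SAP*

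**What the plan says.** SAP Section 9.2.1.4 defines three groups.

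- **Positive:** at least two positive samples "up to the time point of interest (i.e., excluding Baseline, excluding SFU) regardless of other" negative, missing or inconclusive results.
- **Negative**, by any of three limbs: (1) every sample negative and none missing; (2) a single sample is positive "and all other to the time point of interest (including Baseline) are" negative or missing/inconclusive; (3) "only one sample is missing/inconclusive and the remaining ADA_b samples are negative".
- **Missing:** the remainder, "Defined as study participants who do not fulfil the criteria for one of the 2 groups listed above".

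The section closes by stating that data from Baseline onwards are used to derive the groups.

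Section 9.2.2.2 uses the groups for ASAS40 and ASAS20 response over time, in figures and in a table. For the figures it adds that if at least 95% of "study participants are included in the non-missing groups, the missing group will not be displayed on the figure".

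The overall ADAb status in Section 9.2.1.2 follows a different convention. One positive sample is enough for positive, and among participants with no positive it applies a one-sample tolerance: "Missing if the study participant has missed more than one" result.

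**The concern.** Two features of the definitions do not fit together.

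First, a detected antibody lowers the evidence needed to be called negative. With no positive sample, a second missing sample sends the participant to Missing. With one positive sample, any number may be missing and the participant stays negative. A rule that requires two positives to show persistence could explain calling a fully sampled single positive negative. It does not explain doing so when the samples that would show persistence are absent.

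Second, the two definitions count over different sets of samples. Baseline does not count towards positive but does count in limb (2), which leaves a gap between them.

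At stake is the response-by-antibody-status comparison. Under non-responder imputation (Section 4.2.1.3), a participant with one positive sample who stops treatment before Week 16 and gives no later sample enters the negative group as a non-responder.

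**Working it through.** **Inputs.** The schedule in Section 2.2.4 gives Baseline plus 4 samples to Week 16, 6 to Week 24 and 8 to Week 52. Code each sample P (positive), N (negative) or M (missing or inconclusive), in the order Baseline, Weeks 4, 8, 12, 16. Limb (2) can be read two ways. In reading A the single positive may be the Baseline sample. In reading B the words on Baseline require Baseline itself to be negative or missing.

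**Labels under Section 9.2.1.4**

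| Pattern | Post-Baseline P | All P | M | Group |
|---|---|---|---|---|
| N-P-M-M-M | 1 | 1 | 3 | Negative |
| N-N-M-M-M | 0 | 0 | 3 | Missing |
| P-P-N-N-N | 1 | 2 | 0 | Missing |
| P-N-N-N-N | 0 | 1 | 0 | A: Negative; B: Missing |
| P-P-P-N-N | 2 | 3 | 0 | Positive |

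P-P-N-N-N has too few countable positives for the positive rule and too many for limb (2). Under Section 9.2.1.3 the same participant is Category 4 or 5, depending on titer, and Category 5 counts as treatment-emergent.

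**How wide the gaps are, to Week 16** (3^5 = 243 possible patterns)

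- Limb (2), reading A: 5 × 2^4 = 80 patterns. Those with none or one missing number 5 × (1 + 4) = 25, so 55 have two or more missing.
- Limb (2), reading B: 4 × 16 − 4 × 5 = 44 have two or more missing.
- Up to 4 of the 5 samples may be missing.
- Complete-data patterns labelled Missing: 4 (A) or 5 (B) to Week 16, 6 or 7 to Week 24, and 8 or 9 to Week 52.
- Baseline-positive patterns: 3^4 = 81. Positive: 81 − 16 − 32 = 33. Of the other 48, reading A gives 16 Negative and 32 Missing; reading B gives 48 Missing.

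These count possible patterns, not expected participants.

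**Effect on the contrast.** The SAP gives no counts, so the following are assumed, for the 200 planned bimekizumab participants:

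- 150 negative, 75 responders;
- 34 with two or more positives, 14 responders;
- 6 with a single positive and several missing samples;
- 10 with no positive who stopped early (Missing; non-responders by imputation).

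| Assumption and handling | Negative | Positive | Difference (points) |
|---|---|---|---|
| The 6 stopped, as written | 75/156 = 48.1% | 14/34 = 41.2% | 6.9 |
| The 6 sent to Missing | 75/150 = 50.0% | 41.2% | 8.8 |
| The 6 counted positive | 50.0% | 14/40 = 35.0% | 15.0 |
| The 6 counted positive, the 10 kept negative | 75/160 = 46.9% | 35.0% | 11.9 |
| The 6 left negative, the 10 also kept negative | 75/166 = 45.2% | 41.2% | 4.0 |
| The 6 stayed and 4 responded, as written | 79/156 = 50.6% | 41.2% | 9.5 |
| The 6 stayed and 4 responded, counted positive | 50.0% | 18/40 = 45.0% | 5.0 |

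The rows with the 6 stopped show limb (2) shrinking the contrast. The last two rows show it enlarging the contrast. Sending the 10 antibody-negative stoppers to Missing also enlarges it (6.9 against 4.0).

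More generally, let a share q of the negative group hold one positive sample and respond like positives. The observed difference is then (1 − q) × the true difference. With assumed rates of 45% and 25%, q = 5%, 10%, 20% and 30% turn 20 points into 19, 18, 16 and 14.

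**The case against.** A reader might infer that the definitions hide an antibody effect and that the bias always runs towards no effect. The SAP does not support that. Inconclusive samples include those with drug concentration above the assay tolerance limit (Section 9.1.1), so limb (2) can also take in participants still on treatment, some of whom may respond. Sending antibody-negative stoppers to Missing pushes the contrast the other way.

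Other points in the plan's favour also stand:

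- Requiring two positives for the efficacy groups is an analysis choice, so differing from the overall status in Section 9.2.1.2 is not in itself a contradiction.
- Section 9.2.2.2 also plots response by titer quartile and plans individual plots grouped by the categories of Section 9.2.1.3. Neither uses these groups. The quartile plots do rely on the titer at the given visit, so they cannot place a participant without that sample.
- An early-termination antibody sample is mapped to the next antibody visit (Section 3.2.3), and participants who stop treatment are encouraged to keep attending (Section 2.3). A second positive obtained this way makes the participant Positive. This narrows the first gap but does not close it.
- The 95% display rule covers the figures. The percentage in each group is still summarised, and the response table carries no such rule.
- Baseline-positive participants with two or more later positives are correctly Positive.
- The summaries are descriptive, with no planned test.

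None of this repairs the wording. N-P-M-M-M is still negative, and P-P-N-N-N is still Missing with nothing missing.

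**Conclusion.** The definitions in Section 9.2.1.4 are internally inconsistent and give wrong labels in two identifiable situations: one positive sample with several missing, and Baseline positivity with exactly one later positive. A participant positive only at Baseline gets a label that depends on how limb (2) is read, so two programmers could produce different tables. These conclusions rest on the text and the sampling schedule alone.

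The effect on the response comparison is less certain. Single-positive participants who stop and give no later sample attenuate an antibody effect. The net size and direction depend on how many such participants there are, how many single positives stay on treatment and respond, and how many antibody-negative stoppers go to Missing. The SAP gives none of these, and the percentages above are illustrations. The primary analysis and the testing hierarchy are not affected.

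**What to change.** Change Section 9.2.1.4 in two places and add one display.

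1. Use one Baseline rule in both definitions, either post-Baseline samples only or Baseline included in both. Every participant with complete data then has either at least two countable positives (Positive) or at most one (Negative).
2. Limit limb (2) to at most one missing/inconclusive sample and send the rest to Missing. Early stoppers with one positive and with none are then handled alike.
3. Add one sensitivity display of ASAS40/ASAS20 response in which any post-Baseline positive sample makes the participant ADAb positive.

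The cost is SAP wording, one extra table and a few more participants in Missing. No new data are needed.

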9.2.1.5 ADAb Sample Inclusion and Exclusion Rules

The following rules will be implemented for by-visit ADAb summaries and apply to all visits except Week 52, ET and SFU:

- From Baseline through Week 24 Visit, if the ADAb sample is collected within ± 14 days relative to the visit date at which BKZ was administered (or ± 14 days from a scheduled visit at which BKZ dosing was not performed), the ADAb result for that sample will be associated with the scheduled visit and summarized accordingly.
- After the Week 24 Visit, if the ADAb sample is collected within ± 21 days relative to the visit date at which BKZ was administered (or ± 21 days from a scheduled visit at which BKZ dosing was not performed), the ADAb result for that sample will be associated with the scheduled visit and summarized accordingly.
- The two rules described above will include unscheduled assessments as described in Section 3.1 if a dose was administered at the unscheduled visit.

Samples collected outside the relevant windows described above will be excluded from the ADAb by-visit summaries and will be listed only.

For samples associated with the Week 52, ET or SFU visits, all ADAb data obtained will be included in the by-visit summaries.

All other summaries of ADAb status (as described in the previous section) will use all available (scheduled and unscheduled) data.

The reason for exclusion will be assigned as one or more of the following:

- Sample collected out of window relative to current dose (or visit)
- More than one sample obtained at the same visit

